D.9.6. Future developments in HCV treatment. Study participants will receive state-of-the-art treatment (IFN in combination with telaprevir and ribavirin). As additional regimens become available with either more convenient dosing, fewer side effects, or increased efficacy, participants in all 3 arms will receive treatment according to best available practices. On October 10, 2014, the FDA approved fixed-dose (ledipasvir and sofosbuvir). Because rates of SVR are >95% in patients initiating treatment with fixed-dose (ledipasvir and sofosbuvir), all newly enrolled subjects will initiate treatment with this regimen. It is likely that our intensive models of care will be generalizable to IFN-sparing regimens which include only oral therapies. We recognize that HCV treatment has been greatly simplified, but issues with adherence, resistance, side effects, and cost will remain.

D.10. Data sources and collection.

D.10.1. Overview. Sources of data will include: blood and urine tests, participant interviews, medical charts, staff activity and expense logs, direct observation of staff, and electronic adherence monitors (Table 3).

D.10.2. Research visits. Research visits will occur at baseline, then every 4 weeks during the first 12 weeks of treatment, then at week 24 (if necessary), a “Final Treatment Week visit” will be conducted after the last day of treatment, and then post-treatment visits after 4, 12, and 24 weeks, for a total of up to 9 research visits. Participants will receive \$25 for each visit and an additional \$20 for visits with blood draws.

Baseline visit (Table 3). At baseline we will assess: sociodemographic and HCV clinical factors, potential mediating variables based on the IMB model, potential moderators (including psychiatric status, substance use, and unstable housing), and additional psychosocial factors hypothesized to predict adherence. The baseline visit will take approximately 3 hours. Blood will be collected at the first visit and stored for possible HCV viral load and resistance testing, and for future studies.

Follow-up visits (Table 3). Follow up visits will occur at weeks 4, 8, 12, and 24 (if necessary).

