Adherence to all medications will be evaluated by electronic monitors and self-report. Weeks on treatment will be determined by electronic monitors and chart review. HCV viral load, virological endpoints, and resistance results will be obtained by chart review and blood draw, if unavailable by chart review. IMB model mediators will be assessed at weeks 8 and 12. Potential moderators will be assessed at each monthly visit.

Table 3. Overview of Data Collection by Aims

Aim & Hypothesis	Construct	Measure, source	Research visit (week)	Source
Outcome Measures				
Aim 1, H1	Adherence	Med-ic® and MEMS® Electronic Monitors	4,8,12	Electronic
Aim 1, H2	Completion	Medical record	NA	Chart
Aim 1, H3	Viral load (SVR)	HCV VL by Roche TaqMAN assay	0,4,8,12, 24, FU 4, FU12, FU24	Chart, Blood
Aim 1/2, H4	Resistance	HCV GenoSURE NS3/4A, NS5A, NS5B (Monogram)	4, 8, 12, 24, FU4, FU12, FU24	Chart, Blood
Aim 3	Cost	HCV treatment mDOT and CGT interventions Non-HCV treatment health services	NA NA 12,24, FU4, FU12, FU24	Chart Logs, Direct Observation Q
Other covariate measures*				
All	Demographics	Age, race/ethnicity, education, income, housing	0	Q
All	HCV-related clinical information	HCV VL, HIV, HCV genotype/subtype, IL28B, APRI and FibroSURE (biomarkers of liver fibrosis)	0	Chart
All	Substance use	Addiction severity Index-Lite (ASI-lite) (152,153) Alcohol use (AUDIT) (154) Urine toxicology EMIT assay	0,4,8,12, 24, FU4, FU12, FU24	Q, Urine
All	Methadone dose opiate withdrawal	Methadone dose; Subjective and Objective Opiate Withdrawal Scales (SOWS and OOWS) (155)	0,4,8,12, 24, FU4, FU12, FU24	Q
All	Neuropsychiatric	MINI (138-140)	0	Q
All	Information, motivation, and behavioral Skills	Health Beliefs Model (161) HCV Motivation (161) Adherence Self-Efficacy (161)	0, 12	Q
All	Social support	Medical Outcomes Scale (162)	0,4,8,12,24, FU4, FU12, FU24	Q
All	DAA levels	GC-MS (if additional funding obtained)	4	Blood
All	Depression, anxiety, and hostility	Depressive symptoms (BDI-II) (156-157) Brief Symptom Inventory (BSI) anxiety subscale (158) BSI hostility subscale (158-160)	0,4,8,12,24, FU4, FU12, FU24	Q
All	Psychosocial factors	Stages of readiness for HCV treatment (183) Trust in physician (184)	0 0,4,8,12,24, FU4, FU12, FU24	Q
All	Quality of life	HCV QOL and EQ-5D (163-166)	0,4,12, 24, FU4, FU12, FU24	Q
All	Med side-effects	Adult ACTG adherence instrument – revised (167)	0,4,8,12, 24, FU4, FU12, FU24	Q

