All	Adherence (self report)	Adult ACTG adherence instrument (167) Visual Analogue Scale (VAS) (168) 24 hour dietary recall instrument	0,4,8,12,24	Q

Q=Questionnaire

*All measures used in [name] pilot K23 HCV DOT study or [name] current R01 study

D. 10.3. Definitions of outcome measures.

Med-ic® or MEMS® missed dose adherence. For DAA and ribavirin (if applicable), adherence will be calculated as Med-ic blister pack dose openings divided by total number of prescribed doses in time interval. For example, Med-ic adherence for one week would be X/7Y, where X=number of Med-ic dose openings recorded in one week and Y=number of doses prescribed per day.

HCV treatment completion. Subjects will be considered to have completed treatment if they have completed at least 80% of the planned treatment course (at least 10 weeks of 12 week course, or at least 20 weeks of 24 week course) based on response guided therapy approach.^{98,115}

Sustained viral response (SVR). SVR is defined as undetectable HCV viral load 12 weeks after treatment completion or discontinuation.

Resistance. Subjects will be considered to have new drug resistance if they have a telaprevir- associated mutation (any substitutions at V36, T54, R155, A156) at any time point during the study, and the specific mutation did not exist at baseline. Subjects will be considered to have new drug resistance if they have a ledipasvir- associated mutation (K24R, M28T/V, Q30E/H/K/L/R, L31V/M/I, and Y93H/N) during the study, and the specific mutation did not exist at baseline. Subjects will be considered to have new drug resistance if they have a sofosbuvir- associated mutation (S282T) at any time point during the study, and the specific mutation did not exist at baseline.

Cost. Costs of HCV treatment will be collected using the same methods as in the pilot analysis (see Section D.1.8 above), by conducting chart reviews and assigning unit costs to all provider visits, lab tests, and medications based on Medicare fee schedules. The cost of the mDOT intervention will be determined by conducting observational time studies of the additional medical provider and patient time required for mDOT,

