ADHERENCE TO DAAs AND RIBAVIRIN will be measured in all three arms by electronic compliance monitoring for blistered medications for the first 12 weeks of treatment with an attached Med-ic® device. Med-ic® is an innovative stick-on paper label for medication blisters that provides a disposable method to measure adherence.¹⁸⁵ Med-ic® packages yield 99.6% event accuracy (time of dose removal correctly recorded within ± 2 minutes). This technology will allow tracking of medication usage from weekly blister packs prepared by our local pharmacist. Blister packs will be pre-fitted with labels and electronic tags, which can be recycled up to five times to save cost.

In the TAU arm, subjects will receive monthly packages of 4 blister packs, delivered at their methadone clinic by nurses. Blister packs will be returned at research visits for downloading adherence data. In the CGT arm, subjects will receive weekly blister packs at group meetings and used packs will be collected at each group. Unreturned packs will be returned at research visits.

In the mDOT arm, subjects will take observed doses from weekly blister packs, but the packs will be modified to contain only observed doses. Individual take-home doses will be taken in weekly blister packs given on Monday. Blister packs will be collected weekly.

SELF-REPORT ADHERENCE will be measured using a modified ACTG questionnaire, adapted for IFN, DAAs, and ribavirin, as well as a single-item visual analogue scale (VAS) which has been shown to correlate well with both pill counts and virological outcomes in HIV-infected patients taking HAART.^{167,168} Adherence to dietary recommendations will be conducted by 24 hour dietary recall. Fat content of each meal will be determined with available software (www.nutritionco.com).

Participant surveys. At baseline and every research visit, participants will answer surveys using Audio Computer-Assisted Self-Interview (ACASI) technology. The ACASI system displays each question on a computer monitor while playing an audio recording of the question. Participants enter responses directly on the computer, which may result in more accurate reporting of sensitive behavior than other survey methods.¹⁷⁰

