For the analysis of repeatedly measured adherence (using 6 post-baseline time points and adherence as a continuous measure), we will apply mixed effects linear model to test if the 3 groups are significantly different. This model accounts for within-subject longitudinal outcome correlation by taking the subject-level intercept as random. The model will include potential confounding variables. If the omnibus equality test is rejected, we will conduct the 2 post-hoc pairwise tests described above. Concerning potential clustering effects in the CGT arm, we used pilot data (5 groups) to examine whether clustering influenced adherence. Between cluster variation was not significant, as tested by application of a random effects repeated-measure ANOVA model. Clustering in the GCT arm will be minimal, and we will not adjust for it in statistical or power analysis.

We will also apply mixed effects logistic regression to test the significance of mDOT and CGT on repeatedly-measured undetectable HCV VL throughout the intervention period, adjusting for substance use. Changes in illicit drug use will be analyzed using urine toxicology data from each visit, counting the “person-month” as a unit of analysis, and analyzing the proportion of person-months that are positive for use of illicit drugs using a chi-square analysis.

As secondary analyses, we will examine if mDOT and CGT effects, v. TAU, will be mediated by IMB components. We will assess IMB model mediators of adherence at baseline, and during the intervention, and will analyze changes in those variables from the baseline to the intervention period. The indirect effects of IMB mediators will be tested by assessing changes in coefficients of the intervention effect (mDOT or CGT) with and without IMB component(s) in mixed effects models. Confidence intervals of the mediated effects will be calculated by bootstrapping, and mediation assumed if confidence intervals do not include zero.

D.12.3. Hypotheses for Aim 2. We hypothesize that only a minority (~20%) of IDUs will develop resistance, and that the relationship between adherence and resistance will be quadratic.

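### The schedule for the IMB mediator scales contradicts itself on week 8, and if Table 3 is followed no on-treatment mediator value precedes any of the electronic adherence it should explain

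*Combined protocol and SAP*

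**What the plan says.** **Mediator schedule, text.** The baseline paragraph of D.10.2 includes "potential mediating variables based on the IMB model". The follow-up paragraph says "IMB model mediators will be assessed at weeks 8 and 12". Read together, the text schedule is weeks 0, 8 and 12.

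**Mediator schedule, Table 3.** The information, motivation and behavioral skills row reads "Health Beliefs Model (161) HCV Motivation (161) Adherence Self-Efficacy (161) 0, 12 Q". Week 8 is absent.

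**Adherence.** Table 3 gives "Med-ic® and MEMS® Electronic Monitors 4,8,12 Electronic". D.10.4 describes "electronic compliance monitoring for blistered medications for the first 12 weeks of treatment". D.10.3 defines the measure as "Med-ic blister pack dose openings divided by total number of prescribed doses in time interval", so each value looks back over the interval just ended.

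**Analysis.** D.12.2 states: "We will assess IMB model mediators of adherence at baseline, and during the intervention". It analyses change in the IMB variables from baseline to the intervention period and compares the arm coefficient in mixed models with and without the IMB components. It takes mediation as shown when the bootstrap confidence interval excludes zero. No time lag is specified. The analysis is labelled secondary.

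**The concern.** The IMB model, as set out in B.9, runs in one direction: information, motivation and skills determine adherence. A mediation analysis supports that direction only if the mediator is measured before at least some of the outcome. A patient who has just taken nearly all doses for 12 weeks may well report higher self-efficacy and motivation because of it. If the arms differ in adherence, such a score also differs by arm and correlates with adherence within arm. The arm coefficient then shrinks when the score enters the model, just as it would under true mediation.

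The planned test of the framework behind both interventions could therefore be read as support when the scores are only a consequence of adherence. The practical risk is in data collection. If the week-8 interview is built from Table 3, the scales will be left out and those data cannot be recovered.

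**Working it through.** The documents give no sample size, power or error rate for the mediation analysis, so there is no figure of the plan's own to reproduce.

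**Step 1: the two schedules against the adherence intervals.** Electronic adherence is collected at weeks 4, 8 and 12, which gives three intervals: 0–4, 4–8 and 8–12.

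| Source | IMB weeks | First post-baseline value | Share of 12-week window elapsed | Intervals that follow it |
|---|---|---|---|---|
| Table 3 | 0, 12 | week 12 | 12/12 = 100% | 0 of 3 |
| D.10.2 text | 0, 8, 12 | week 8 | 8/12 = 67% | 1 of 3 (weeks 8–12) |

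Under Table 3, a change from baseline can be formed only at week 12. That value would be set against adherence in three intervals that are all over.

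**Step 2: how often the D.12.2 rule would mislead.** This is an illustration with no true mediation.

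- From D.13: 40 completers per arm, standardised arm effect d = 0.6, ICC 0.5 (the upper value given there).
- Assumed: one intensive arm against TAU; a constant effect over three intervals; adherence Y averaged over the intervals; later IMB score M = gY + noise of variance 1. The slope g is the feedback from adherence to the score. The documents give no value for it, so it is shown as a range.
- Rule: change in the arm coefficient with and without M, by least squares on subject means as a stand-in for the mixed model, with a percentile bootstrap interval. 400 simulated trials and 200 bootstrap samples per value of g.

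The apparent proportion mediated has a closed form. The within-arm variance of Y is v = 0.5 + 0.5/3 = 0.667, and the proportion is g²v / (1 + g²v). For g = 0.5 this is 0.25 × 0.667 / (1 + 0.25 × 0.667) = 0.167/1.167 = 14.3%.

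| g | Mediation declared | Apparent proportion, simulated | Closed form |
|---|---|---|---|
| 0 | 0.5% | 0% | 0% |
| 0.3 | 9% | 7% | 5.7% |
| 0.5 | 23% | 14% | 14.3% |
| 0.8 | 48% | 30% | 29.9% |

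The Monte Carlo standard error at 23% is √(0.23 × 0.77/400) = 2.1 points. Because the simulated proportion at g = 0.3 lay above the closed form, the simulation was repeated with 2,000 trials and 400 bootstrap samples. It declared mediation in 0.2%, 6%, 24% and 46% of trials. The pattern is the same, and the g = 0.3 figure is best read as 6 to 9%.

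The baseline for comparison is the g = 0 row, not 5%. With no link between adherence and score, this test is very conservative.

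**Step 3: what adjustment for earlier adherence would do.** Take weeks 8–12 as the outcome and adjust for mean adherence over the first two intervals, with the same d and ICC. The variance of that mean is 0.5 + 0.5/2 = 0.75 and its covariance with the third interval is 0.5, so the slope is 0.5/0.75 = 0.667. The arm effect left is 0.6 × (1 − 0.667) = 0.20. By simulation, power to detect it is about 17 to 19% with 40 per arm and 21% with 50.

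**The case against.** Much can be said for the plan, and most of it stands.

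- *Baseline is covered.* A reader of the follow-up sentence alone might infer that the text leaves out baseline. It does not: the baseline paragraph of D.10.2 includes the IMB variables. The sources differ on week 8 only.
- *Not every adherence measure precedes week 12.* A reader might infer that the mediator always comes after adherence. Table 3 also lists self-reported adherence at week 24, a visit held only if needed, so on a 24-week course one self-report point can follow the week-12 scales. Social support, which Table 2 places under motivation, is measured at every visit. The ordering problem is strict for the three IMB scales against electronic adherence, and for 12-week courses.
- *Six adherence points.* D.12.2 refers to six post-baseline adherence points, which might suggest monitoring beyond week 12. Table 3 lists three electronic points and D.10.4 limits electronic monitoring to 12 weeks, so the six do not rescue the ordering. That mismatch needs settling too.
- *Table 3 is not the whole cause.* Under the text schedule two of three intervals are already over at week 8, and D.12.2 specifies no lag. Correcting the table alone leaves much of the problem.
- *The rates rest on an assumed slope.* This is correct, so no single rate should be quoted.
- *The analysis is secondary.* Mediation appears in none of the three aims and not in the Aim 1 hypotheses.

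What does not fall away is the contradiction on week 8, and the fact that week 8 is the only visit in either schedule where an on-treatment IMB score precedes any electronic adherence.

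**Conclusion.** The point holds as a minor one. The text and Table 3 disagree on week 8. If Table 3 governs, the mediation analysis of electronic adherence has no on-treatment value of the three IMB scales that precedes the outcome, and it cannot tell mediation from feedback.

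The size is conditional. With d = 0.6, ICC 0.5 and 40 per arm, false declarations of mediation run from under 1% without feedback to nearly half of trials at slope 0.8, and nothing in the documents says where in that range the truth lies. A reader might infer that the mediation result is bound to be spurious, or that the trial's main conclusions are at risk. The documents support neither: feedback may be weak, and the arm comparisons do not use the IMB scores.

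**What to change.** 1. Change the Table 3 IMB row to 0, 8, 12, to match D.10.2.
2. Add to D.12.2 a time-ordered sensitivity analysis that relates IMB change from week 0 to week 8 to electronic adherence in weeks 8–12. Describe it as exploratory and low in precision, and say that adherence before week 8 may still influence the week-8 score.
3. Do not make adjustment for adherence through week 8 the main mediation analysis. It conditions on a post-randomisation variable that the interventions are meant to change and, under the assumptions above, leaves about a third of the arm effect (0.20 of 0.6). It can be reported beside the unadjusted result.
4. Reconcile the six adherence points in D.12.2 with Table 3 in the same edit.

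The cost is three scales at a week-8 computer interview that already takes place, plus a few sentences of analysis text. The gain is limited: one of three adherence intervals follows the week-8 measure, so the ordering problem is reduced and not removed.

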1. **To determine in a randomized trial whether either of two intensive on-site HCV treatment models (DOT or concurrent group treatment) provided at a methadone program is more efficacious than standard on-site treatment for enhancing adherence and virological outcomes, and decreasing drug resistance.** We will compare the proportion of subjects in each arm who: a) adhere to antiviral treatment; b) complete antiviral treatment; c) attain SVR (cure); and d) develop drug resistance.
2. **To determine the incidence and factors associated with the development of drug resistance in IDUs initiating HCV treatment.** In a pooled analysis of all subjects, we will determine what proportion of subjects develops resistance, and examine associations between adherence and resistance.
3. **To perform cost and cost-effectiveness analyses of each model of intensive on-site HCV care.** We will use empirical data to determine the total costs of providing intensive on-site or standard on-site care. A computer simulation cost-effectiveness model combining empirical and published data will be used to determine dollars per quality-adjusted life-year gained associated with intensive versus standard care.

B. SIGNIFICANCE

B.1. HCV epidemic in IDUs. HCV prevalence in injection drug users (IDUs) ranges from 70-90%, and HCV incidence ranges from 10–26 per 100 person-years.¹⁻⁴ IDUs comprise 60% of all HCV-infected persons in the U.S., and genotype-1 infections are the most prevalent (74%).⁵ In the U.S., approximately 35,000 acute HCV infections occur each year, and a 4-fold increase in the number of adults with chronic HCV is projected from 1990-2015.⁶ HCV causes up to 15,000 deaths annually, and is the leading cause of liver transplantation in the U.S.⁷⁻⁹ Until recently (6/11), HCV treatment was effective in less than 50% of patients in registration trials,¹⁰⁻¹² and much less effective (14%) in real-world urban populations.¹³ Treatment effectiveness among IDUs is crucial because IDUs remain the leading risk group for HCV infection.¹⁴

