D.1.8. Cost pilot data. Drs. [name] and [name] conducted a retrospective chart review of costs of HCV treatment for patients treated in a methadone maintenance program. Mean treatment costs were \$40,600 for patients with SVR and \$31,400 for patients without SVR. Drs. [name] and [name] conducted a study of health care services utilization by HCV-infected patients in the AIDS Clinical Trials Group Longitudinal Linked Randomized Trials Cohort¹³⁶ in which they described the additional use of hospital and emergency department services associated with HCV infection in this cohort after adjusting for demographic and clinical factors. [name] has also assessed the cost of HIV medication adherence support interventions.¹³⁷

D.2. Overview of study approach. In the proposed study, 150 HCV-monoinfected IDUs (genotype 1) eligible for on-site HCV treatment will be recruited from opiate agonist treatment clinics and randomized to one of 3 models of care: modified directly observed treatment (mDOT); concurrent group treatment (CGT); or standard on-site treatment which represents the treatment as usual arm (TAU). We will compare the proportion of patients in each arm who optimally adhere (>80%), complete treatment, achieve SVR, and develop resistance. We hypothesize that both intensive models of care (mDOT and CGT) will be superior to TAU. Participants on 48 week regimens (e.g. telaprevir) will be followed for 72 weeks (up to 48 weeks of HCV treatment + 24 weeks of follow-up), with visits occurring every 4 weeks for the first 24 weeks, followed by 4 additional visits at 12 week intervals. Participants (n=100) on 12 – 24 weeks regimens (fixed-dose ledipasvir and sofosbuvir) will be followed up to 48 weeks (up to 24 weeks of HCV treatment + 24 weeks of follow-up) with visits occurring every 4 weeks for the first 12 weeks, week 24 (if necessary), end of treatment, and follow-up weeks (4, 12 and 24). Data sources will include blood tests (HCV viral load and resistance tests), urine toxicology tests, questionnaires, medical records, electronic monitors for assessing adherence, and staff logs and direct observation (for cost-effectiveness analysis). In pooled analyses of all subjects (n=150), we will determine associations between adherence and development of resistance. We will also assess cost and cost-effectiveness of all 3 models.

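### The SVR and resistance definitions do not separate relapse from reinfection, so an uncertain share of the few expected ledipasvir/sofosbuvir failures could be misclassified

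*Combined protocol and SAP*

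**What the plan says.** Section D.10.3 sets the efficacy endpoint: "SVR is defined as undetectable HCV viral load 12 weeks after treatment completion or discontinuation". Any detectable virus at that point is therefore a failure, whatever its source. (Section B.2 describes SVR at 24 weeks; D.10.3 is the operative definition.)

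The same section defines new resistance by listed substitutions. For ledipasvir it requires a "mutation (K24R, M28T/V, Q30E/H/K/L/R, L31V/M/I, and Y93H/N) during the study, and the specific mutation did not exist at baseline". For sofosbuvir it requires an "associated mutation (S282T) at any time point during the study, and the specific mutation did not exist at baseline". The telaprevir rule has the same form.

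Table 3 schedules resistance assessment at weeks 4 to 24 and at follow-up weeks 4, 12 and 24 (FU4, FU12, FU24). It lists genotype/subtype at week 0 only. On baseline material, Section D.10.2 says: "Blood will be collected at the first visit and stored for possible HCV viral load and resistance testing".

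Three figures bear on size:
- Section B.1: "HCV incidence ranges from 10–26 per 100 person-years".
- Section D.9.6: "rates of SVR are >95% in patients initiating treatment with fixed-dose (ledipasvir and sofosbuvir").
- Section D.2: "Participants (n=100) on 12 – 24 weeks regimens".

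The documents never mention reinfection. They plan no repeat subtyping or sequence comparison for recurrent viraemia.

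**The concern.** Participants come from a population with continuing exposure. Someone cleared by treatment and then reinfected before FU12 is recorded as an SVR failure. If the new strain carries a listed substitution that the old one lacked, the rule also records new drug resistance, although no study drug selected it.

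On a regimen with few true failures, a few such events could matter in four places:
- the comparison of observed SVR with registration trials (D.12.1, D.13);
- the arm comparison of SVR and resistance (Aim 1);
- the adherence–resistance curve (Aim 2), where a fully adherent, cured and then reinfected participant would appear as resistance at high adherence;
- the SVR and resistance inputs to the cost-effectiveness model (Aim 3).

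**Working it through.** **The plan's own figure.** The documents give no reinfection figure. Their only design figure for this endpoint is SVR power above 80% (D.13), with 70%, 70% and 40% and 40 completers per arm. For the three-group chi-square test, noncentrality = n Σ(pᵢ − p̄)² / [p̄(1 − p̄)] = 40 × (0.01 + 0.01 + 0.04) / 0.24 = 10.0. On 2 df, with alpha 0.05 (assumed for the omnibus test), power is 81.5%. The stated figure reproduces.

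**Reinfection risk.** r = 1 − exp(−incidence × weeks/52), with incidence 0.10 to 0.26 per person-year (B.1).
- 12 weeks: 2.28% and 5.82%.
- 24 weeks: 4.51% and 11.31%.

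**Share of apparent failures due to reinfection.** With true failure rate f, share = (1 − f)r / [f + (1 − f)r]. For 100 participants and f = 5% (the edge of SVR above 95%), 95 × r gives 2.2 to 5.5 reinfections by FU12, against 5 true failures. The shares are 2.2/7.2 = 30% and 5.5/10.5 = 53%. Observed SVR would be 92.8% to 89.5% instead of 95%.

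| Scenario at FU12 | Share |
|---|---|
| f = 5%, 10–26 per 100 PY in everyone | 30–53% |
| f = 5%, only 30% of participants at risk | 12–25% |
| f = 5%, only 49% at risk | 18–35% |
| f = 5%, 2–5 per 100 PY (assumption) | 8–18% |
| f = 3%, 10–26 per 100 PY | 42–65% |
| f = 10%, 10–26 per 100 PY | 17–34% |
| f = 20%, 10–26 per 100 PY | 8–19% |
| f = 40%, 10–26 per 100 PY | 3–8% |

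The 30% and 49% are illicit drug use during treatment, and in the 6 months before it, in an earlier on-site cohort (D.1.3). The 40% is the mean failure at the planned SVR rates: (30 + 30 + 60)/3.

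**False resistance calls.** A reinfection counts only if the new strain carries a listed substitution absent at baseline. The documents give no such frequency for NS5A; B.7 gives 5% baseline variants in telaprevir trials. Assuming 5–15%, false calls per 100 by FU12 run from 2.2 × 0.05 = 0.1 to 5.5 × 0.15 = 0.8. For scale, B.7 reports resistance-associated mutations in 62% of failures with earlier agents. Borrowing that figure gives 5 × 0.62 = 3.1 true cases, so false calls would be 0.1/3.2 = 3% to 0.8/3.9 = 21% of the total.

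**Arm contrast.** If reinfection multiplies every arm's SVR by (1 − r), the planned 30-point difference becomes 29.3 to 28.3 points. Omnibus power falls from 81.5% to 79.2% (10 per 100 PY) or 75.4% (26 per 100 PY). At 2–5 per 100 PY it is 81.1–80.4%.

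**The case against.** The strongest objection is that the high shares stack unfavourable assumptions. A reader might infer that about half of ledipasvir/sofosbuvir failures will be reinfections. That needs 26 per 100 person-years, that hazard in every cured participant, and only 5% true failure. The quoted incidence is for people who inject drugs in general. Trial participants attend a methadone clinic at least weekly, and the clinic's mean age is 47. The SVR above 95% is a regimen figure, whereas the protocol warns of lower adherence and more discontinuation in this population. This part stands. Half is not a strict ceiling either, because true failure below 5% raises the share.

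A reader might also infer that any new mutation counts as resistance. The rule is narrower: only listed substitutions absent at baseline count, so most reinfections would be read as relapse and not as resistance. If resistance reached the roughly 20% expected in D.12.3, fewer than one false case per 100 would be negligible.

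Nor can it be assumed that follow-up to FU24 doubles the exposure window for resistance. Over 24 weeks the share of viraemia would be 46–68% at f = 5% and the quoted incidence. But D.10.4 ties post-treatment resistance testing to absence of SVR, while Table 3 and the automatic assay at 2000 IU/ml or above point the other way. Whether someone with SVR at week 12 would be assayed later is unclear.

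Finally, the definition of SVR is not itself an error, and D.13 already treats the arm comparison of resistance as exploratory. That also stands. None of it supplies a rule for telling relapse from reinfection.

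**Conclusion.** The gap is real and its size is uncertain. Under milder incidence assumptions with 5% true failure, reinfection is about 8–35% of FU12 viraemia. It reaches 30–53% only if everyone carries the quoted incidence, and falls to 3–8% if SVR is as low as the power section plans. False resistance calls are likely to be about 1 per 100 or fewer by FU12, on the assumed 5–15% carriage. They matter mainly because resistance events on this regimen should be few.

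It would be tempting to conclude that the SVR comparison between arms is biased. The documents give no reason to expect reinfection to differ by arm, so the supported conclusion is dilution, with a modest loss of power. The comparison with registration trials is more exposed: there, reinfection lowers observed SVR directly, by 2.2 to 5.5 percentage points at the quoted incidence and 5% failure.

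**What to change.** Add to D.10.3 and D.12.4:

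1. For each participant with documented undetectable virus at end of treatment or FU4 who is later viraemic, compare baseline and post-treatment subtype and NS3/4A, NS5A or NS5B sequences. Use stored baseline blood and the post-treatment resistance assay, and classify by a sequence-distance threshold fixed in advance. Subtype alone cannot separate relapse from reinfection with the same subtype.
2. Do not count substitutions from a different strain as new drug resistance in Aims 1d and 2.
3. Keep SVR at 12 weeks as the primary definition. Add a sensitivity analysis that counts reinfection after documented clearance as treatment success.
4. Pass the reinfection count to the Aim 3 model.
5. Reconcile Table 3 with D.10.4 on whether resistance is assayed at FU24 after SVR at week 12, and on which regions are run: Table 3 lists NS3/4A, NS5A and NS5B, while D.10.4 names only NS3/4A.

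The cost is a handful of baseline sequences. At 5% true failure there would be about 5 to 11 viraemic participants by FU12 (5 + 0.4 to 5 + 5.5), and fewer with prior documented clearance. The resistance rule's "at any time point during the study, and the specific mutation did not exist at baseline" already needs a baseline sequence, so part of this work is implied. The downside is slightly fewer resistance events for Aim 2.
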